#### 10.1.2. Definite treatment failure

A definite treatment failure occurs when a patient with baseline PMD between -2 and -3.5dB experiences a decline of > or equal to 2dB which remains after repeat perimetry.

Study Number: INVEX-CLIN-IIH-301 Protocol	Compound No.: Presendin
	Version: 5.0 for EU countries dated 08Dec2022

Or in those with a baseline PMD between -3.5 and -7 dB who experience a decline of > or equal to 3 dB which remains after repeat perimetry.

These cases should be reviewed without delay by the IAC (who will review all visual and clinical data) to confirm or refute a definite treatment failure.

## **10.2. Rescue Therapy/Rescue Intervention for Progressive Visual Loss**

When a treatment failure occurs, rescue therapy can be initiated, in addition to study treatment, based on the medical judgement of the Investigator. Decisions should always be discussed with the IAC without delay and if possible before any action is taken, unless in the opinion of the Investigator there is no time to do so as it is judged to be a medical emergency. In all cases the final decision lies with the Investigator.

Patients showing progressive visual loss will be considered for rescue therapy with acetazolamide or an alternative diuretic. In cases where the visual loss is severe and “rapid”, and believed by the Investigator to necessitate surgical intervention, the intervention will be conducted in accordance with local emergency practice.

### **10.2.1. Rescue Therapy for Headache**

If the Investigator wishes to alter the headache preventative medication (any drug can be considered), this decision should always be discussed with the IAC before any action is taken, unless in the opinion of the Investigator there is no time to do so as it is judged to be a medical emergency. Use of headache preventative medication will be recorded at trial visits.

Use of acute headache analgesics is not considered as rescue medication and is permitted but must be documented in the headache diary (monthly analgesic use).

## **11. CONCOMITANT MEDICATIONS AND NON-DRUG THERAPIES**

### **11.1. Recording Prior and Concomitant Medication**

All relevant medication taken within 4 months of screening should be recorded in the eCRF along with all relevant medication taken from the start of the screening period until the final follow-up visit (Section [6.2.1.3](#)).

Study Number: INVEX-CLIN-IIH-301 Protocol	Compound No.: Presendin
	Version: 5.0 for EU countries dated 08Dec2022

At a minimum the following information will be collected:

- Generic name
- Dose
- Frequency
- Date started
- If ongoing (or if not, then the date stopped will be recorded)
- Reason for taking the medication

## 11.2. Prohibited Medications

### 11.2.1. Prior to screening and randomisation

- Treatment to lower ICP within 1 week prior to screening (e.g., acetazolamide, topiramate (including if used as a migraine preventative), diuretics, glucocorticoids (I.V., injectable steroids or oral (including dexamethasone and prednisolone)). (Nasal, inhaled, or topical steroids are allowed).
- Exposure to fluoroquinolones, lithium, vitamin A, or tetracyclines within 2 months of diagnostic LP
- Glucagon like peptide-1 receptor agonist within last 4 weeks prior to screening
- Warfarin
- Glucose-lowering medication COVID-19 vaccine within 2 weeks prior to screening
- Recreational or illicit drugs during screening period

Note: Use of headache preventative medication is allowed at enrolment (except for Topiramate). Changes to headache preventative medication during the trial should be made in consultation with the IAC – see section [10.1.2](#).

Study Number: INVEX-CLIN-IIH-301 Protocol	Compound No.: Presendin
	Version: 5.0 for EU countries dated 08Dec2022

### 11.2.2. During the trial

- Treatment to lower ICP (e.g., acetazolamide, topiramate (including if used as a migraine preventative), diuretics, glucocorticoids (I.V., injectable steroids or oral (including dexamethasone and prednisolone)). (Nasal, inhaled, or topical steroids are allowed). These will all be considered rescue medication (Section 10.1.2) and the IAC consulted. Use will be considered a protocol deviation.
- If the Investigator alters the headache preventative medication (including oral or botulinum toxin A or monoclonal antibodies against CGRP or CGRP antagonists, or greater occipital nerve block) this will be considered headache rescue medication (Section 10.1.2) and the IAC consulted.
- Glucagon like peptide-1 receptor agonists
- Recreational or illicit drugs
- Warfarin
- Glucose-lowering medication
- Regarding COVID-19 vaccination, the risks of receiving or not receiving the vaccination have been considered in relation to the IMP and no additional risks are envisaged. Hence patients may choose to have or not have COVID-19 vaccination or booster during this trial.

The investigator should follow the cautions and guidance on the management of other concomitant medication or DDIs as detailed in section 9.2.5.2 (Drug-Drug Interactions) of the IB.

## 12. PATIENT COMPLETION AND WITHDRAWAL

### 12.1. Patient Completion

Patients will be classed as having completed the trial once they have completed all required trial visits. See Section 11.2.1 for early discontinuations.

Study Number: INVEX-CLIN-IIH-301 Protocol	Compound No.: Presendin
	Version: 5.0 for EU countries dated 08Dec2022

## 12.2. Patient Withdrawal

### 12.2.1. Patient Withdrawal from Trial Treatment

A patient will be withdrawn from treatment for any of the following reasons:

- Withdrawal of consent to continue in the trial. The reason for this will be documented if provided
- The Investigator or Sponsor, for any reason, decides the patient should be withdrawn from the treatment
- Lack of compliance with the trial medication is classified as <75% or >125% of scheduled doses over the course of the trial, excluding supply issues
- Adverse events, which cannot be tolerated by the patient
- Pregnancy during the treatment period
- Retroactive failure to fulfil inclusion/ exclusion criteria (in this clinical drug trial designated phase III), if individual Benefit/Risk does not overrule
- New medical conditions not allowing for continuation of the protocol conform treatment
- Enrolment in any other clinical trial involving an investigational product, or enrolment in any other type of medical research judged not to be scientifically or medically compatible with this study
- If the patient, for any reason, requires treatment with another therapeutic agent that has been demonstrated to be effective for treatment of the study indication
- If the patient, for any reason, requires treatment with a concomitant medication that during this trial should be avoided for reasons of safety and/or efficacy reasons
- Any code breaking/unblinding requested by the investigator
- Protocol-mandated permanent discontinuation of the investigational study treatment

Patients will be encouraged to continue in the trial to the end of the randomised treatment period even if they stop trial medication so that data can be collected for the Intention-To-Treat (ITT) population.

If a patient is withdrawn from treatment during the randomised treatment period, they will be encouraged to return for all trial visits up to visit 10. If a patient does not want to return then at a minimum they should be encouraged to attend for visit 11 procedures as a safety follow-up visit.

Study Number: INVEX-CLIN-IIH-301 Protocol	Compound No.: Presendin
	Version: 5.0 for EU countries dated 08Dec2022

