## PROTOCOL SUMMARY

### Rationale

Idiopathic intracranial hypertension (IIH) is a condition characterised by raised intracranial pressure (ICP) with unknown aetiology, occurring most frequently in obese women of childbearing age. IIH is a rare condition; however, incidence is increasing with rising obesity trends.

IIH has significant associated morbidity and reduced quality of life. Elevated ICP causes papilloedema universally at disease onset and can lead to permanent visual loss. Visual loss occurs in greater than 90% of those with IIH [Wall 1991] and can be severe and permanent in between 5-25%. Besides risk of visual loss, the most disabling aspect for patients is severe chronic headaches driven by elevated ICP. Existing pharmacotherapies are limited. The most frequently used drug therapy, acetazolamide, is used off label and has been shown to have efficacy but due to side effects and treatment failures new drugs are needed. Surgical therapy to lower ICP is a last resort and used as an emergency procedure to save vision but the failure rates are high and frequent complications and side effects occur.

A modified release formulation of exenatide (Presendin) has been developed and this trial has been designed to evaluate the efficacy and safety of Presendin in IIH. The modified release formulation has been chosen to enable a once weekly dosing.

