## 1. INTRODUCTION

### 1.1. Background and Rational

Idiopathic intracranial hypertension (IIH) is a condition characterised by raised intracranial pressure (ICP) with unknown aetiology, occurring most frequently in obese women of childbearing age. IIH is a rare condition; however, incidence is increasing with rising obesity trends [Mollan, 2019a]. There is a high rate of repeat hospital admission in IIH (increased by 446% in last decade), reflected in escalating healthcare costs (in England £462 million/year predicted by 2030 [Mollan, 2019a] and more than \$444 million in the USA [Friesner, 2011]).

The cause of IIH is not fully understood. Recent research suggests that IIH is a disease of systemic metabolic dysregulation characterised by central adiposity [Hornby, 2017], double the risk of cardiovascular disease in excess to that mediated by obesity [Adderley, 2019] and dysfunctional adipocyte metabolism primed for weight gain [Westgate, 2021]. Patients are also insulin resistant and have a unique hormone signature of androgen excess both systemically and in the cerebrospinal fluid.[O'Reilly, 2019]

Morbidity in IIH is due to the elevated intracranial pressure which can cause severe papilloedema (swelling of the optic nerve) which can ultimately lead to blindness. The risk of permanent visual loss is a major concern in IIH. Visual loss occurs in greater than 90% of those with IIH [Wall 1991] and can be severe and permanent in between 5-25%. Headache is an additional major disabler and affects the majority of IIH patients (over 90%) [Yri, 2014; Markey, 2016; Mulla 2015] in the long term. Headaches significantly reducing quality of life [Mulla, 2015; Digre, 2015] are driven by raised intracranial pressure and often have a migraine- like phenotype (> 90%) [Mollan 2021a].

Existing pharmacotherapies are limited. The most frequently used drug therapy, acetazolamide, is used off label and has been shown to have efficacy but due to side effects and treatment failures new drugs are needed. [Piper, 2015; Mollan, 2018; Hoffmann, 2018]. Surgical therapy to lower ICP is a last resort and used as an emergency procedure to save vision but there is a high failure rate and frequent complications. The lack of licenced or targeted treatments in IIH perpetuates poor outcomes for patients. A priority setting exercise was run by patients with IIH (James Lind methodology) [Mollan, 2019c] establishing effective therapy was the top priority from the patient group.

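### Protocol Version 5.0 tells investigators both to continue and to stop study drug when ICP-lowering rescue medication is given (10.2 against 12.2.1)

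*Protocol*

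**What the plan says.** Section 10.2, the rescue section, states: "When a treatment failure occurs, rescue therapy can be initiated, in addition to study treatment, based on the medical judgement of the Investigator". It then names the drugs: "Patients showing progressive visual loss will be considered for rescue therapy with acetazolamide or an alternative diuretic". Section 4.1.1 likewise describes medical rescue as adding an ICP-lowering drug, with surgery as the alternative.

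Section 12.2.1 opens its list with "A patient will be withdrawn from treatment for any of the following reasons". Two entries matter here:

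- Reason A: "If the patient, for any reason, requires treatment with another therapeutic agent that has been demonstrated to be effective for treatment of the study indication".
- Reason B: the patient "requires treatment with a concomitant medication that during this trial should be avoided for reasons of safety and/or efficacy reasons".

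Section 1.1 states of the named rescue drug: "acetazolamide, is used off label and has been shown to have efficacy". The Rationale in the protocol summary says the same. Section 11.2.2 puts acetazolamide, topiramate, diuretics and glucocorticoids among the medications prohibited during the trial, calls them rescue medication, requires the adjudication committee to be consulted, and classes their use as a protocol deviation.

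**The concern.** An investigator who starts acetazolamide after a confirmed treatment failure cannot comply with both sections. Section 10.2 has study drug continuing alongside rescue. Section 12.2.1 takes the patient off study drug and makes no exception for rescue. Nothing in the protocol says which section prevails.

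The decision falls when a patient's vision is deteriorating, so the instruction should be unambiguous. If investigators resolve it differently, similar patients will have different study-drug exposure after rescue, and different entries for whether and why study drug was stopped. Section 14.3.1.1.1 expects more use of ICP-lowering medication on placebo, so the affected patients are unlikely to be split evenly between arms.

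**Working it through.** The point is textual. The only arithmetic is the expected number of patients.

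**Step 1. Does the named rescue drug meet the withdrawal reasons?**

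| Withdrawal reason in 12.2.1 | What the protocol says of the drug | Met? |
|---|---|---|
| A: another agent demonstrated effective in the indication | Sections 1.1 and Rationale credit acetazolamide with efficacy; 14.2.3.1 cites a placebo-controlled acetazolamide trial with a 5.9 cm CSF reduction and significant PMD improvement | Yes, for acetazolamide |
| B: a concomitant medication to be avoided | 11.2.2 lists ICP-lowering treatment, including acetazolamide and diuretics, as prohibited during the trial | Yes, for any drug in that class |

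Reason A applies whatever the cause of the need. Reason B is enough by itself, so the conflict does not depend on how strictly A is read.

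**Step 2. Does any text resolve it?** No exception for rescue appears in 12.2.1, and no precedence is stated. The cross-reference does not help: 11.2.2 sends the reader to Section 10.1.2 for rescue, but in Version 5.0 that section defines definite treatment failure. Rescue is in 10.2.

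**Step 3. Comparison with Version 4.0, bound in the same file.** Its section 10.1.2 has the same provision for rescue on top of study treatment. Its withdrawal list in 11.2.1 has neither reason A nor reason B. Within this file, the contradiction therefore appears only in Version 5.0. The cross-reference to 10.1.2 is correct under Version 4.0 numbering.

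**Step 4. How many patients?** Inputs: 120 per arm (14.2.1); 6 treatment failures among 79 placebo patients in the earlier acetazolamide trial, and a predicted 6.7% on placebo here (both 4.1.1).

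- The stated rate does not follow from its source: 6/79 = 7.6%. A figure of 6.7% would need about 6/90.
- At the stated rate: 120 × 0.067 = 8.0 placebo patients.
- At the rate from 6/79: 120 × 0.0759 = 9.1 placebo patients.

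No rate is given for the Presendin arm, so no count is offered there. These are patients needing rescue of any kind. Both withdrawal reasons concern an agent or a medication, so a patient treated by surgery alone may meet neither.

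**Step 5. Which data does study-drug status after rescue reach?**

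- Week-24 ICP in anyone who used ICP-lowering medication is removed and imputed (14.3.1.1.1). PMD, OCT and MHD values after its start are removed and imputed (14.3.1.2.1, 14.3.1.3.1, 14.3.1.4.4). Little reaches these analyses.
- Patient-reported outcomes are analysed as observed (14.3.5), so values after rescue stay in.
- Exposure after rescue, and adverse events on study drug plus rescue or on rescue alone, depend directly on the rule followed.
- Section 14.3.6 makes imputation depend on the reason data are missing, and brings in additional treatment events for the secondary estimands. Whether rescue entails a mandated discontinuation changes what is recorded and which patients have such an event.

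**The case against.** The strongest reply is that 10.2 is the specific rescue provision and should govern over a general withdrawal list, especially as 11.2.2 itself calls these drugs rescue and routes them through the adjudication committee. That is a reasonable way to read intent, and committee discussion could reduce variation. But 12.2.1 is worded as mandatory, has no exception, and is not made subordinate to 10.2 anywhere. Reason A can also be contested, since 4.1.1 describes such drugs as unlicensed and only potentially pressure-lowering. Reason B is unaffected.

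The second reply is that the statistical damage is small. This largely stands, and it rules out several stronger inferences a reader might draw:

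- *That the primary comparison is biased between arms.* The primary estimand applies regardless of adherence (14.3.1.5), and the affected values are removed in both arms.
- *That the safety denominator or per-protocol set changes.* The Safety population needs only one dose. Prohibited medication and rescue procedures are already listed as deviations to be considered for per-protocol exclusion (14.3.2).
- *That the secondary estimand is materially altered.* It too assumes no medication likely to affect ICP or PMD (14.3.1.6), so the issue there is consistent event definitions.
- *That this is the commonest planned intercurrent event.* No ranking is given, and there are no rates for off-protocol lumbar punctures or headache-preventative changes.
- *That 12 to 24 of 240 patients are caught.* This would apply the 5–10% in section 1.1 to both arms, but that figure concerns patients needing more aggressive intervention and is not a rate of medical rescue.

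**Conclusion.** The contradiction in Version 5.0 is real. For a patient given ICP-lowering rescue medication, 10.2 has study drug continue and 12.2.1 requires it to stop. Handling may therefore vary between investigators and sites; the documents do not show that it will. It may also vary by protocol version if Version 4.0 is still in force somewhere. Both versions are in the file, but nothing shown establishes concurrent use, so a regional difference in the rule is a possibility only.

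The size is about 8 to 9 of 120 placebo patients, assuming the 6.7–7.6% rate carries over, less any rescued by surgery alone. The consequences lie in study-drug exposure and safety data after rescue, patient-reported outcomes, recorded discontinuation reasons, and above all the clarity of instructions to sites. The ICP, PMD, OCT and MHD analyses are largely protected by removal and imputation.

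**What to change.** 1. Reconcile 10.2, 11.2.2 and 12.2.1 into a single rule for study drug once ICP-lowering rescue medication starts. The sponsor's clinical team should choose it; no view is offered here on which rule is right. The text should also say how surgery-only rescue is treated.
2. Correct the reference in 11.2.2 to Section 10.1.2 so that it points to the rescue section, which is 10.2 in Version 5.0.
3. Align the list of discontinuation events used for the secondary estimand, and the reasons for missingness that 14.3.6 leaves to the SAP, with the chosen rule.
4. If Version 4.0 is in force anywhere, apply the same rule there.

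The cost is amendment wording, a memo to sites and a consistency check of the SAP event list. Sample size, visits and the primary analysis are unchanged.

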### **12.3. Treatment after the End of the Trial**

Patients will not be provided with trial medication following the end of the trial.

### **12.4. Screen and Baseline Failures**

Information will be collected on all patients who sign the Informed Consent Form (ICF).

## **13. ADVERSE EVENTS**

### **13.1. Definitions**

#### **13.1.1. Adverse Events**

An AE is any untoward medical occurrence in a patient or clinical investigation patient administered a pharmaceutical product and which does not necessarily have a causal relationship with this treatment. An AE can therefore be any unfavourable and unintended sign (including an abnormal laboratory finding), symptom, or disease temporally associated with the use of a medicinal (investigational) product, whether or not related to the medicinal (investigational) product.

#### **13.1.2. Adverse Drug Reactions**

In the pre-approval clinical experience with a new medicinal product or its new usages, particularly as the therapeutic dose(s) may not be established: all noxious and unintended responses to a medicinal product related to any dose should be considered adverse drug reactions. The phrase responses to a medicinal product means that a causal relationship between a medicinal product and an adverse event is at least a reasonable possibility, i.e. the relationship cannot be ruled out.

#### **13.1.3. Serious Adverse Events or Serious Adverse Drug Reactions**

An SAE is any untoward medical occurrence that at any dose:

- Results in death
- Is life-threatening
- Requires inpatient hospitalization or prolongation of existing hospitalization
- Results in persistent or significant disability/incapacity

Study Number: INVEX-CLIN-IIH-301 Protocol	Compound No.: Presendin
	Version: 5.0 for EU countries dated 08Dec2022

- Is a congenital anomaly/birth defect

Medical and scientific judgement should be exercised in deciding whether reporting is appropriate in other situations, such as important medical events that may not reach the above definition but may jeopardise the patient or may require medical or surgical intervention to prevent one of the other outcomes listed in the above definition. These should also be considered serious. Examples of such events are invasive or malignant cancers, intensive treatment in an accident and emergency department or at home for allergic bronchospasm, blood dyscrasias or convulsions that do not result in hospitalisation, or development of drug dependency or drug abuse.

Deterioration of IIH necessitating CSF shunting or optic nerve sheath fenestration or dural venous sinus stenting will be recorded as an SAE and reported.

Deterioration of IIH necessitating hospital admission will be recorded as an SAE and reported.

Pre-defined exclusions:

- Hospitalisation for unrelated elective procedures
- Post LP headache

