### Intracranial pressure

IIH is a debilitating condition characterised by raised ICP, which is clinically measured by LP [Mollan, 2018]. The units for measurement of LP are cm CSF and cm H2O and these should be thought of as interchangeable and reflect the measurement of the height of the CSF column at LP. The measurement must be taken in the lateral decubitus position. Lumbar puncture is conducted to make a diagnosis of IIH. Lumbar puncture may be conducted in a clinical setting during the disease course to both monitor and treat the condition. Frequent therapeutic LPs are no longer recommended by the International IIH guidelines [Mollan, 2018]. This is because LP can be traumatic for patients and can occasionally cause significant complications (meningitis, spinal haematoma, pain) [Wright, 2012]. Hence, unnecessary LP's should be avoided. In some patients LP can alter other outcome measures, including measurements of papilloedema and headache [Yiangou, 2019]. Hence ideally, LP should be performed after these measures and symptoms have been assessed. Lumbar puncture can cause post-dural puncture headaches. The risk is 9-36% using a traumatic needle and 3-19% using an atraumatic needle [Wright, 2012]. Post-dural puncture headaches typically last less than a week but in some patients this can be longer [Yiangou, 2019]. Lumbar puncture pressure assessment of ICP reflects disease activity and is a useful and recognised outcome measure that has been utilised in other IIH trials [Markey 2020; Mollan 2021b].

Due to the invasive nature of LP, non-invasive measures of ICP are valuable. The majority of techniques historically evaluated as non-invasive surrogate measures of ICP lack sufficient quantification to be used clinically or in clinical trials. Optical coherence tomography (OCT) measures of the optic nerve have been shown to provide a useful surrogate measure to quantify changes in ICP [Vijay, 2020]. For example, at 12 months, Vijay *et al* showed that a change in optic nerve head height of 50  $\mu$  predicted a 5 cm CSF change in ICP [Vijay, 2020].

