### 13.3. Severity Criteria

An assessment of severity grade will be made using the following categorical descriptors:

- Grade 1 means a relatively minor side effect
- Grade 2 means a moderate side-effect
- Grade 3 means a severe or medically significant but not immediately life-threatening side-effect
- Grade 4 means life-threatening consequences
- Grade 5 death related to AE

The exact definition of each number in the scale depends on the particular side effect according to Common Terminology Criteria for Adverse Events (CTCAE) v5.0 [[CTCAE](#)].

The Investigator should use clinical judgment in assessing the severity of events not directly experienced by the patient (e.g., laboratory abnormalities).

Study Number: INVEX-CLIN-IIH-301 Protocol	Compound No.: Presendin
	Version: 5.0 for EU countries dated 08Dec2022

Adverse events occurring as a result of LP should be specifically recorded. Occurrence of post lumbar headache will be specifically reported.

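### Section 13.1.3 excludes post-LP headache from SAEs without limit, so a headache that meets a seriousness criterion loses SAE status and immediate reporting

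*Protocol*

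**What the plan says.** Section 13.1.3 opens broadly: "An SAE is any untoward medical occurrence that at any dose" meets one of the listed criteria, whether or not the drug caused it. One criterion is "Requires inpatient hospitalization or prolongation of existing hospitalization". The section ends with a short list headed "Pre-defined exclusions", which has two entries. One carries its own limit: "Hospitalisation for unrelated elective procedures". The other reads only "Post LP headache". Version 4.0 of the protocol, bound in the same file, has the same two entries in its section 12.2.

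Other sections also deal with the event. Section 13.3 asks for adverse events caused by LP to be recorded specifically and adds: "Occurrence of post lumbar headache will be specifically reported". Section 13.4 requires every adverse event, serious or not, to be entered in the eCRF with a causality opinion. Section 13.4.1 requires immediate reporting to the sponsor's designee, and its wording covers SAEs only.

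Appendix 1 separates the diagnostic LP, which is routine care, from the LP at Week 24 (Visit 10), which is done for the trial. On headache after LP, section 1.1 (Intracranial pressure) states: "The risk is 9-36% using a traumatic needle and 3-19% using an atraumatic needle".

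**The concern.** The definition and the exclusion pull against each other. A patient admitted with headache after the Week 24 LP meets the hospitalisation criterion, yet the exclusion says the event is not an SAE. A site following the text literally would file it as non-serious.

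What is at stake is classification and speed. SAE status is what triggers immediate notification under section 13.4.1 and onward reporting to authorities and ethics committees. The LP concerned is imposed by the trial, and it falls at the last scheduled treatment-period visit. Table 1 puts Visit 10 on Day 169 and Visit 11, by default a telephone call, on Day 204, a gap of 204 - 169 = 35 days. Immediate reporting is therefore worth more here than it would be between closely spaced visits.

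**Working it through.** This is mainly a comparison of texts; the plan has no figure of its own to reproduce.

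**Step 1: which events the exclusion acts on**

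| Post-LP headache | SAE by the definition? | SAE after the exclusion? | Effect of the exclusion |
|---|---|---|---|
| Meets no seriousness criterion | No | No | None |
| Meets a criterion, e.g. admission | Yes | No | SAE status removed |

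The line changes the outcome only in the second row. Reading it as aimed at ordinary, non-serious headache leaves it with no function.

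**Step 2: whether another section restores SAE status**

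- Section 13.3 secures specific recording and reporting, with a severity grade, as an adverse event. It says nothing about SAE status.
- Section 13.4 secures entry in the eCRF regardless of seriousness. It does not reclassify the event.
- Section 13.4.1 gives the immediate route, for SAEs only.

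None of the three undoes the exclusion.

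**Step 3: what is not excluded**

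The list names headache alone. Meningitis and spinal haematoma, which section 1.1 mentions as LP complications, are not on it and are SAEs if a criterion is met.

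**Step 4: rough size**

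Inputs:
- Completed Week 24 LPs (section 14.2.1.1, Intracranial Pressure Power): 60 per arm if 50% are missing, 2 x 60 = 120; 72 per arm if 40% are missing, 2 x 72 = 144.
- Headache risk (section 1.1): 9-36% with a traumatic needle, 3-19% with an atraumatic needle.
- Share admitted: not in the protocol. Assumed 1-10%.

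Expected headaches = LPs x risk:
- Traumatic: 120 x 0.09 = 10.8 to 144 x 0.36 = 51.8.
- Atraumatic: 120 x 0.03 = 3.6 to 144 x 0.19 = 27.4.

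Expected admissions = headaches x assumed share:
- Lowest: 3.6 x 0.01 = 0.04.
- Highest: 51.8 x 0.10 = 5.2.

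The range is about 0 to 5 admissions. Most of the 4 to 52 headaches would meet no criterion under that assumption, so the exclusion would make no difference to them. The count of admissions is the one that matters.

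**The case against.** The strongest reply is that little is lost. A headache after the Week 24 LP begins after first dosing, so it is treatment-emergent. It is graded under section 13.3, entered in the eCRF under section 13.4, and tabulated by severity under section 14.3.4.1. The Data Safety Monitoring Committee reviews safety data every six months (section 15.7), and nothing shown confines it to SAEs. Visit 11 may be held in clinic for adverse events still ongoing at end of treatment. Section 1.1 adds that these headaches usually last less than a week.

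All of this stands, and it rules out several stronger readings that a reader might infer:

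- *That serious harm from the research LP in general escapes SAE reporting.* Only headache is excluded. Section 13.4 also asks for the diagnosis, where possible, when signs share a cause, so a headache that proves to be meningitis or haematoma would be reported under that diagnosis.
- *That the event is hidden from the sponsor or the committee.* It reaches the eCRF and the adverse event tables, and may reach the committee as safety data.
- *That a needle, technique or site problem could not be detected.* Clustering could still be seen in the adverse event data, where section 13.3 specifically requires this event.

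The reply does not remove the contradiction within section 13.1.3. Adverse event capture is a backstop; it does not supply SAE status or the immediate report that goes with it.

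**Conclusion.** The point holds in a narrow form. As written, section 13.1.3 removes SAE classification, and with it the immediate reporting of section 13.4.1, from any post-LP headache that meets a seriousness criterion, such as one leading to admission after the Week 24 research LP. The conflict is in the text and depends on no numerical assumption.

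The size is uncertain and probably small. The figure of about 0 to 5 patients rests wholly on the assumed 1-10% admission share, on the protocol's own headache risks, and on 120 to 144 completed Week 24 LPs. The primary endpoint and its analysis are unaffected. The point is worth correcting because the procedure is imposed by the trial and the correction is simple.

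**What to change.** Reconcile the exclusion with the SAE definition in section 13.1.3. Limit it to post-LP headache that meets no seriousness criterion, and state that post-LP headache meeting any listed criterion, including causing or prolonging admission, is recorded and reported as an SAE under section 13.4.1. Make the same change in section 12.2 of version 4.0 wherever that version is still in use.

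The cost is one sentence and, on the range above, a few more SAE forms. Routine post-LP headache stays outside SAE reporting, and no visit, endpoint or analysis changes.
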